# 4.3. Identity of Investigational Product:

International Non-proprietary name

Manufacturer

Dose

Telaglenastat
Calithera
As per protocol

Route of Administration oral

Formulation Capsule or tablet formulation (200 mg)

Telaglenastat will be provided by Calithera.

For oral administration only

Store at room temperature 15-30°C (59-86° F). Do not refrigerate or freeze. Keep bottle tightly closed.

The Expiry date will be provided by Calithera (based on Certificate of Analysis)

## 4.4 Supportive Care Guidelines and Concomitant Medications:

4.4.1. Concomitant treatment is permitted if the medication is not expected to interfere with the evaluation of safety or efficacy of the study drug. During the study, if the use of any concomitant treatment becomes necessary (e.g., for treatment of an adverse event), the treatment must be recorded on the eCRF, including the reason for treatment, name of the drug, dosage, route, and start and stop dates of administration

NCT ID: NCT03047993

Protocol 2016-0636 ate: 06/03/2019

Page **17** of **39** 

- 4.4.2. Supportive measures including blood and platelet transfusions, antimicrobials, and analgesics are permitted.
- 4.4.3. The administration of anticancer therapies, other investigational cytotoxic agents, or prophylactic use of hematopoietic colony stimulating factors are not permitted.
- 4.4.4. Erythropoietin or hematopoietic colony stimulating factors for treatment of cytopenias are **discouraged**. If administered, the subject will not be eligible for a HI response assessment within one week of the receipt of epoetin alfa or filgrastim, tbo-filgrastim, filgrastim-sndz, or for one month after receipt of pegfilgrastim or darbopoetin.
- 4.4.5. Telaglenastat is metabolized by human hepatocytes primarily through amide hydrolysis. Telaglenastat does not appear to induce CYP drug-metabolizing enzymes and only weakly inhibits CYP2C9 (IC $_{50}$  1.8-6.7  $\mu$ M) *in vitro*. Therefore, drug-drug interactions are not expected. Although CB-839 is not expected to inhibit CYP2C9 at the exposure levels planned, caution is warranted when administering CB-839 to patients taking drugs that are highly dependent on CYP2C9 for metabolism and have a narrow therapeutic index. (See Appendix A).

Preliminary PK data generated in this and concurrent Phase 1 studies suggest that concomitant use of agents that increase gastric pH (e.g., proton pump inhibitors, H2-receptor antagonists, antacids, etc.) may reduce absorption of telaglenastat, resulting in decreased systemic exposure. Although patients are *not required* to discontinue their use of these agents, discontinuation is recommended whenever possible.

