## Table 2: Procedures during Screening, Staging and Workup

Protocol 2016-063 Date: 06/03/2019

Page **19** of **39** 

	1
Procedures	Specifics
Informed consent	
Full History and Physical Examination	History – present illness, prior surgeries, other medical illnesses, review of systems, allergies, prior therapy for cancer and concurrent meds;
	Physical exam – record weight, and note abnormalities in any major organ system (including but not limited to neurologic, head and neck, lymph nodes, cardiovascular, pulmonary, abdomen, extremities), note and measure sites of disease
Concomitant Medications	
Vital signs (including temperature, pulse, and blood pressure)	
ECOG performance status	NACAL: 7 days with the first days
Urine or blood pregnancy test (females of child-bearing potential only)	Within 7 days prior to first dose
Disease status (IPSS classification and WHO disease classification)	Staging with bone marrow aspiration and biopsy for disease assessment.
Note: Bone marrow aspirate and/or biopsy within 4 weeks prior to first dose of drug in all patients.	
Serum chemistries (repeat if screening chemistries completed greater than 72 hours prior to the first dose)	Sodium, potassium, blood urea nitrogen, creatinine, glucose, calcium, phosphate, magnesium, AST and/or_ALT, total bilirubin, alkaline phosphatase, uric acid, amylase and lipase
CBC with differential (repeat if screening test completed greater than 72 hours prior to the first dose)	Differential may be omitted if WBC ≤0.5 x10  /L
Standard 12-lead EKG with QTc calculation	

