# Response criteria (Responses must last at least 8 weeks)†

Hgb increase by ≥1.5 g/dL Relevant reduction of units of RBC transfusions by an absolute number of at least 4 RBC transfusions/8 wk compared with the pretreatment transfusion number in the previous 8 wk. Only RBC transfusions given for a Hgb of ≤9.0 g/dL pretreatment will count in the RBC transfusion response evaluation†

Absolute increase of ≥30 × 109/L for patients starting with >20 × 109/L platelets Increase from <20 × 109/L to >20 × 109/L and by at least 100%† At least 100% increase and an absolute

increase >0.5 × 109/L† At least 1 of the following:

At least 50% decrement from maximum response levels in granulocytes or platelets

Reduction in Hgb by > 1.5 g/dL Transfusion dependence

Source: (Cheson, et al. 2006) Abbreviations: Hgb indicates hemoglobin; RBC: red blood cell; HI: hematologic improvement. Note: Deletions to the IWG response criteria are not shown. Note: To convert hemoglobin from g/L to g/dL, divide g/L by 10. \*Pretreatment counts averages of at least 2 measurements (not influenced by transfusions) ≥1 week apart (modification).

†Modification to IWG response criteria (Cheson, et al. 2003) ‡In the absence of another explanation, such as acute infection, repeated courses of chemotherapy (modification), gastrointestinal bleeding, hemolysis, and so forth.

For each subject, response to therapy, duration of response, event-free survival, and overall survival will be calculated. The duration of response is defined as the number of

\*Responses must last at least 8 weeks

NCT ID: NCT03047993 Protocol 2016-063 Date: 06/03/2019

Page **25** of **39** 

days from the date of initial response (PR or better) to the date of first documented disease progression/relapse or death, whichever occurs first. Event-free survival is defined as the number of days from the date of treatment initiation (i.e., C1D1) to the date of documented treatment failure, relapses from CR, or death from any cause, whichever occurs first, and will be calculated for all patients. In the event that neither disease progression or death is documented prior to study termination, analysis cutoff, or the start of confounding anticancer therapy, these endpoints will be censored at the

In addition, relationships between anti-tumor activity, PDn markers, exploratory biomarkers, and drug exposure levels will be explored.

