#### 8.1.2. Phase II:

The Simon minimax two-stage design will be employed for the Phase II portion.(15) We assume a target response rate of 60% and a response rate of 40% or lower will be considered not desirable. Response is defined as complete remission (CR), partial remission (PR), marrow CR (mCR), or Hematologic Improvement (HI) by modified IWG criteria for MDS patients. For example a 29% CR/PR rate was reported in the azacitidine arm in the randomized AZA-001 trial, and a 23% CR/PR rate and 60% ORR (including 37% HI) was seen in the azacitidine arm of the CALGB 9221 trial. To implement the Simon's two-stage design, the assessment window for response (CR+PR+mCR+HI) is defined as response occurring within the first 6 cycles of treatment. With a type I error rate of 10% and 80% power, we will enroll 16 patients in the first stage. If 6 or fewer patients achieve response, enrollment will be halted. If 7 or more out of the first 16 patients achieve response, accrual will continue until a total of 28 patients have been enrolled. If 15 or more out of these 28 patients achieve response, the treatment will be considered efficacious and worthy of further investigation. Under this Simon's minimax two-stage design, the probability of early termination is 53% and the expected sample size is 22 if the true response rate is 40%.

Protocol 2016-0636 Date: 06/03/2019

Page **34** of **39** 

A Toxicity Summary will be submitted to the IND Office Medical Monitor after the first 7 evaluable patients and every 7 evaluable patients thereafter.

A Response Summary will be submitted to the IND Office Medical Monitor after 15 evaluable patients complete 6 cycles of study treatment.

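### Hematologic improvement counts as primary response and must last 8 weeks, but section 4.4.4 bars only assessments soon after a growth-factor dose, so the 8 weeks can span growth-factor use

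*Combined protocol and SAP*

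**What the plan says.** **Endpoint.** Section 8.1.2: "Response is defined as complete remission (CR), partial remission (PR), marrow CR (mCR), or Hematologic Improvement (HI"), occurring within the first 6 cycles. Any one component suffices. The HI table in section 6.2.2 is headed "Response criteria (Responses must last at least 8 weeks").

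**Growth factors.** Section 4.4.3 states that "prophylactic use of hematopoietic colony stimulating factors are not permitted". Section 4.4.4 discourages, but does not forbid, erythropoietin or colony-stimulating factors to treat cytopenias. If they are given, "the subject will not be eligible for a HI response assessment within one week of the receipt of epoetin alfa or filgrastim" (the tbo-filgrastim and filgrastim-sndz forms are included), "or for one month after receipt of pegfilgrastim or darbopoetin". Section 4.4.1 requires the drug name, dosage and start and stop dates of concomitant treatment on the eCRF.

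**Baseline for HI.** The footnote in section 6.2.2 reads "Pretreatment counts averages of at least 2 measurements (not influenced by transfusions") and sets them at least 1 week apart. The red-cell transfusion criterion is a reduction "compared with the pretreatment transfusion number in the previous 8 wk", counting only transfusions given for a pretreatment hemoglobin of 9.0 g/dL or less.

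**Schedule.** Table 2 lists "CBC with differential (repeat if screening test completed greater than 72 hours prior to the first dose"). Screening covers the 4 weeks before study drug (section 5.1). Section 5.2.1 implies a further count at C1D1, because hematology is excepted from the 3-day allowance. After Cycle 1, scheduled hematology falls on Day 1 of each cycle (section 5.2.4).

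**The concern.** The two rules use different units. Section 6.2.2 defines HI by a period of 8 weeks; section 4.4.4 protects single assessments. Nothing says whether growth factor given between two permitted assessments voids the HI, interrupts it or leaves it intact. The use that remains allowed, treatment of cytopenias, acts on the same lineages that HI measures.

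This reaches the go/no-go decision. HI can be a large part of response: in one historical azacitidine arm cited in section 8.1.2 it supplied 37 of 60 percentage points. With no control arm, a rise caused by supportive treatment is read as an effect of the combination.

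The baseline gap is separate. The HI criteria need inputs that the screening list does not clearly collect, and no rule says how HI is scored when they are missing.

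**Working it through.** **1. Does the section 4.4.4 bar cover the 8 weeks?** Three consecutive Day 1 visits on a 28-day cycle span 2 × 28 = 56 days, or 8 weeks. An HI can therefore rest on three scheduled counts.

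- *Short-acting agents.* The bar catches a dose only in the 7 days before a count. In each 28-day interval, 28 − 7 = 21 days are outside it; over the 8 weeks, 42 of 56 days.
- *Long-acting agents.* One month is about the full interval between visits, so a dose would usually bar the next Day 1 assessment. The text still does not say whether a barred middle assessment breaks the 8 weeks.
- *Regular dosing.* Short-acting doses a week or less apart keep the patient continuously ineligible. The gap therefore concerns intermittent or recently stopped use.

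**2. Does the schedule supply the baseline?**

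- *Counts.* Section 6.2.2 needs at least two, at least 1 week apart. Table 2 asks for one CBC, repeated only if older than 72 hours, and section 5.2.1 implies one at C1D1. Two counts are likely, but nothing places them a week apart: a screening CBC 2 days before a C1D1 count satisfies Table 2 and fails the footnote.
- *Transfusions.* Section 6.2.2 needs the previous 8 weeks with pre-transfusion hemoglobin. Table 2 asks for a general history and concurrent medications without naming transfusions; screening covers 4 of the 8 weeks, and the eCRF rule in section 4.4.1 applies during the study.

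**3. The design's own figures.** Inputs from section 8.1.2: stage 1 has 16 patients and continues at 7 or more responses; the total is 28, with success at 15 or more; null rate 40%, target 60%. With X₁ ~ Bin(16, p) and X₂ ~ Bin(12, p):

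P(success) = Σ over x = 7 to 16 of P(X₁ = x) · P(X₂ ≥ 15 − x)

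P(early stop) = P(X₁ ≤ 6)

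Expected N = 16 + 12 · [1 − P(early stop)]

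At p = 0.40: success 0.0989, early stop 0.527, expected N = 16 + 12 × 0.473 = 21.7. At p = 0.60: success 0.803. These agree with the stated 10%, 53%, 22 and 80%.

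**4. Sensitivity to false HI.** Let q be the share of true non-responders scored as HI. At a true rate of 40% the apparent rate is 0.40 + 0.60q, and the expected number of false HIs in 28 patients is 28 × 0.60 × q. The q values are assumptions; the documents give none.

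| q | Apparent rate | False HIs in 28 | P(early stop) | P(declared efficacious) |
|---|---|---|---|---|
| 0 | 0.400 | 0 | 0.527 | 0.099 |
| 2% | 0.412 | 0.34 | 0.488 | 0.124 |
| 5% | 0.430 | 0.84 | 0.429 | 0.168 |
| 10% | 0.460 | 1.68 | 0.336 | 0.261 |

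One patient can decide the result. At a true 40%, the chance of exactly 6 of 16, one short of continuing, is 19.8%; the chance of continuing and ending at exactly 14 of 28, one short of success, is 7.4%.

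**The case against.** The protocol has real safeguards. It bans prophylactic colony-stimulating factors, discourages therapeutic use, bars assessment for a week or a month, records dates, and in section 4.4.1 permits only concomitant treatment not expected to interfere with the efficacy evaluation. On this view, reading permission into silence about the 8 weeks is unfair, because a response could equally be held unconfirmed across a period of ineligibility. The mis-scoring rates are also invented, and they apply to every non-responder, including those who never receive growth factor. Finally, denying HI after one brief course could discard a genuine response.

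Much of this stands. The safeguards make exposure uncommon, and the rates are illustrations only. But the safeguards limit use; they do not say how an HI is scored once growth factor has been given. That two readings are both natural shows that the scoring rule is incomplete. The risk to a genuine response is a real cost, reduced if a later clean period can qualify.

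A reader might go further and infer that HI may rest on a single pretreatment count, so that one chance low value creates a response. The documents do not support that. The section 6.2.2 footnote requires at least two counts, section 5.2.1 expects one at C1D1, routine earlier counts are not excluded, and a chance rise would have to persist for 8 weeks. Nor does a missing transfusion history inflate response: without the earlier number, the transfusion route to HI cannot be shown, which loses responses.

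**Conclusion.** The point holds as a gap in scoring a component of the primary endpoint. As written, section 4.4.4 lets an 8-week HI span intermittent or recently stopped growth-factor use, and a supported rise can then count as response. The direction is toward a higher response rate; the size cannot be derived from the documents. The move from 9.9% to 12.4%, 16.8% or 26.1% rests on assumed mis-scoring of 2%, 5% or 10% of non-responders. Given the existing limits on growth-factor use and the 8-week requirement, the actual rate is probably at or below the low end, so the likely effect is small. It still deserves correction, because one patient can change either decision and the correction is cheap.

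The baseline point is lesser: sections 5.1 and 5.2.1 and Table 2 do not secure the one-week spacing or the 8-week transfusion number that section 6.2.2 needs. The consequence is HI that is unevaluable or inconsistently scored, with no clear upward bias.

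**What to change.** **Scoring rule.** Reconcile sections 4.4.4 and 6.2.2 through response scoring only, with no change to who may receive growth factor. Credit HI in a lineage only if the 8-week period that establishes it contains no growth factor acting on that lineage, judged from the start and stop dates already on the eCRF. A later 8-week period free of such treatment can still qualify.

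**Baseline.** In Table 2, record two pretreatment CBCs at least 1 week apart, accepting routine counts, and the red-cell units with pre-transfusion hemoglobin for the 8 weeks before C1D1.

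**Cost.** A wording change and two added CRF items, with an occasional extra CBC where no routine count exists. A few patients may lose HI credit in one lineage or receive it later, which slightly lowers the chance of counting a true responder.

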# 4.5 Dosing Delays and Dose Modifications:

## 4.5.1. Dose Adjustments:

The doses of telaglenastat and AZA will be adjusted according to the guidelines shown in the following tables for study drug-related clinically significant toxicity. If toxicity is not covered in the table, doses may be reduced or held at the discretion of the investigator for the patient's safety.

Patients will be withdrawn from the study if they fail to recover to CTCAE v4.03 grade 0 to 1 (or within 1 grade of starting values for pre-existing laboratory abnormalities) from a clinically significant non-hematologic treatment-related toxicity within 6 weeks (leading to treatment delay of > 4 weeks) unless the investigator feels that the patient should remain in the study because of evidence that the patient is/may continue deriving benefit from continuing study treatment. Such instances will be discussed with the principal investigator on a case by case basis and the discussion documented in the medical record.

Protocol 2016-0636 Date: 06/03/2019

Page **18** of **39** 

Patients with study-drug related toxicities that are manageable with supportive therapy may not require dose reductions. For patients with other drug-related toxicities, the following dose adjustment rules apply:

	NCI CTCAE v4.03 Grade	Action
	Grade 0-2 non-hematological toxicity	No dose reduction.  For grade 2 toxicities that are persistent and/or intolerable (e.g. stomatitis) patients may
		have a treatment interruption or dose reductions to the next lower dose level.
4.5.2.	Grade 3-4 clinically significant non-hematological toxicity†	Hold until recover to NCI CTC AE grade 0-1
		If recovery occurs within 4 weeks after treatment has been held, dose should be reduced to -1 dose level, if applicable.

Administration of subsequent cycles should be administered when neutrophils recover to  $\geq 1 \times 10^{9}$ /L and platelets to  $\geq 30 \times 10^{9}$ /L, or to baseline levels prior to the start of the last cycle of therapy. Patients with residual disease may start the next cycle with neutrophil and/or platelet counts lower than these if judged to be in the best interest of the patient. The decision to treat should be documented in the patient's medical record.

### 5. STUDY PROCEDURES

### 5.1 Screening (Visit 1)

The following procedures are performed during screening, staging and workup. These procedures are to be performed within 4 weeks prior to study drug administration, except where indicated. All procedures for the Phase 1b and Phase 2 are interchangeable.

A signed and dated IEC/IRB approved informed consent form must be obtained before any study specific procedures are performed. Procedures that are part of routine care are not considered study specific procedures. All subjects will be screened for eligibility before enrollment. Once the subject has met all inclusion criteria, they will be enrolled onto the study.

## Table 2: Procedures during Screening, Staging and Workup

Protocol 2016-063 Date: 06/03/2019

Page **19** of **39** 

	1
Procedures	Specifics
Informed consent	
Full History and Physical Examination	History – present illness, prior surgeries, other medical illnesses, review of systems, allergies, prior therapy for cancer and concurrent meds;
	Physical exam – record weight, and note abnormalities in any major organ system (including but not limited to neurologic, head and neck, lymph nodes, cardiovascular, pulmonary, abdomen, extremities), note and measure sites of disease
Concomitant Medications	
Vital signs (including temperature, pulse, and blood pressure)	
ECOG performance status	NACAL: 7 days with the first days
Urine or blood pregnancy test (females of child-bearing potential only)	Within 7 days prior to first dose
Disease status (IPSS classification and WHO disease classification)	Staging with bone marrow aspiration and biopsy for disease assessment.
Note: Bone marrow aspirate and/or biopsy within 4 weeks prior to first dose of drug in all patients.	
Serum chemistries (repeat if screening chemistries completed greater than 72 hours prior to the first dose)	Sodium, potassium, blood urea nitrogen, creatinine, glucose, calcium, phosphate, magnesium, AST and/or_ALT, total bilirubin, alkaline phosphatase, uric acid, amylase and lipase
CBC with differential (repeat if screening test completed greater than 72 hours prior to the first dose)	Differential may be omitted if WBC ≤0.5 x10  /L
Standard 12-lead EKG with QTc calculation	

# 5.2 On-Study Procedures

NCT ID: NCT03047993

Protocol 2016-0636 Date: 06/03/2019

Page **20** of **39** 

# 5.2.1. Cycle 1 Day 1:

Pretreatment baseline procedures are acceptable if performed within 3 days prior to C1D1 except vital signs, serum chemistries, and hematology labs. *Vital signs must be taken prior to dosing on C1D1*. Patients should be instructed not to eat breakfast prior to their clinic visit on C1D1. During the C1D1 visit, patients will undergo the following procedures prior to dosing:

- 1. Symptom-directed physical exam including vital signs and weight. This is a focused exam performed based upon observed clinical signs and patient complaints. System exams are only required as clinically indicated.
- 2. Clinical laboratory evaluation
- 3. Pre-dose plasma sample collection for PK and correlative studies
- 4. Pre-dose bone marrow aspirate and/or biopsy for correlative studies (obtained after study consent is signed).
- 5. Recording of concomitant medications

Telaglenastat should be administered after pre-dose procedures have been completed and the patient has consumed breakfast. Azacitidine will be administered SC or IV after all safety evaluations have been performed and the appropriate premedication has been administered. Note: If institutional guidelines for pre-medication include a proton pump inhibitor (PPI), the treatment should only be administered  $\geq$  1 hour after dosing with telaglenastat . Following receipt of telaglenastat , the patients will undergo the following:

- 1. AE monitoring
- 2. ECG with QTcF (in duplicate) between 2-4 hr post-dose

Subsequent doses of telaglenastat will be self-administered by the patient per dosing instructions after all study procedures have been completed.

# 5.2.2. Cycle 1 Days 2-7:

During Cycle 1 and all subsequent cycles, Days 2-7, patient will undergo vital signs prior to azacitidine administration. Patients may take their telaglenastat doses prior to, during, or after their AZA according to their usual dosing schedule.

#### 5.2.3. Cycle 1 Day 8, Day 15, Day 22 (+/- 3 days)

At these Cycle 1 mid-cycle assessments, patients will return to clinic to undergo the following procedures:

NCT ID: NCT03047993

Protocol 2016-0636 ate: 06/03/2019 Version 1

Page **21** of **39** 

- 1. AE monitoring
- 2. Recording of concomitant medications
- 3. Vital signs and weight
- 4. Symptom-directed physical exam
- 5. Clinical laboratory evaluation (hematology, serum chemistries)
- 6. Plasma samples for PK analysis pre-dose on C1D15
- \*Patients may take their telaglenastat doses prior to, during, or after their clinic visit according to their usual dosing schedule because there are no specified pre-dose procedures *with the exception of C1D15* where the patient should not take their telaglenastat dose prior to arrival due to pre-dose PK sample.

## 5.2.4. Cycle 2 Day 1 (+/- 5 days) and all subsequent cycles on Day 1

Patients may take their telaglenastat doses prior to, during, or after their clinic visit according to their usual dosing schedule because there are no specified pre-dose study procedures *with the exception of C2D1 and C3D1* due to pre-dose PK samples.

- 1. Vital signs and weight
- 2. AE monitoring
- 3. Recording of concomitant medications
- 4. Symptom-directed physical exam
- 5. Clinical laboratory values (hematology, serum chemistry)
- 6. Plasma sample for exploratory biomarker analysis
- 7. Bone marrow evaluation of tumor/disease burden is required for all patients receiving telaglenastat on cycle 2 day 1, cycle 4 day 1, cycle 6 day 1, and every 3 cycles thereafter, +/- 5 days for all above assessments. Additional evaluations are acceptable as clinically indicated.
- 8. Bone marrow sample for biomarker and pharmacodynamics analysis during above protocol-defined time points.
- 9. Plasma samples for correlative analysis on same day as bone marrow sample timepoints are collected
- 10. Plasma samples for PK analysis prior to the administration of study drug, on C2D1 and C3D1.

